18.1 Translational Medicine Details

a. Background

Combined therapeutic checkpoint blockade of cytotoxic T-lymphocyte antigen 4 (CTLA-4, ipilimumab) and programmed death 1 protein (PD-1, nivolumab) has demonstrated higher objective response rates when compared to either ipilimumab or nivolumab as single agents in advanced melanoma patients but is associated with increased toxicities (Grade 3/4 treatment-related adverse events of 55%). (1)

A key challenge in oncology today is how to select for patients that are likely to respond to single agent anti-PD1. Furthermore, in patients unlikely to respond to single agent anti-PD1, it remains unclear which patients are likely to benefit from combined ipilimumab/nivolumab. Immunodiagnosics that predict and monitor response will be key to addressing this challenge and are urgently needed considering the number of combinations entering oncology in the next 5 years. (2)

To date, no immune assay has been adopted in the clinic to assist with clinical decision-making. We propose to systematically investigate the predictive utility of four immunodiagnostic approaches that measure distinct parameters within tumors: i) quantitative multiplexed immunohistochemistry (qmIHC) which provides spatially resolved, multiparametric information and measures the density, location and phenotype of immune cell types (Tumeh et al. nature 2014); ii) immunosequencing of the T-cell receptor (TCR) repertoire which is based on bulk reads and measures the clonality and repertoire of TCRs (Tumeh et al. nature 2014); and iii) whole exome sequencing which generates signal based on bulk measurements and identifies all non-synonymous mutations (Shin et al. Cancer Discovery 2017); and iv) RNASeq which, through analysis of mRNA expression levels, can identify changes in the functional characteristics of different cells in the tumor microenvironment (Hugo et al. Cell 2016). These approaches have shown preliminary predictive potential by independent groups across different cancer types. (3,4,5) No study to date, however, has investigated the relationship between these factors or their predictive value when interrogating the same tumor. By defining the relationships between these four factors in terms of response, we anticipate that our approach will lead to clinically actionable information as well as key insights into why certain tumors are immunogenic and others are not.

Data storage and computational infrastructure: To optimally perform computational analysis on the large amount of genomic and imaging data to be generated from this study, it is expected that appropriate cloud computing infrastructure with the necessary analysis pipeline is required for the storage and computation of these data. One such computational infrastructure and resource available for this study is through the collaboration with the Parker Institute for Cancer Immunotherapy.

Objective 1: To compare the predictive value of four baseline tumor factors: T-cell density, T-cell receptor (TCR) clonality mutational load, mRNA and other phenotypical expression levels, and circulating tumor DNA. The following provides information about the methods for each approach. Samples will be obtained within 28 calendar days of starting combined ipilimumab/nivolumab for analysis (or, if not feasible, obtained at any point since documented progression on PD-1 or PD-L1

therapy alone). Critical to understanding how these antibodies promote tumor rejection is the identification of immune cell types that are altered during therapy. Samples obtained during treatment will also be analyzed in order to understand how distinct immune cell types evolve in terms of density, effector activity, proliferative status and cell:cell proximity during intervention according to response. Additionally, we will investigate how the T-cell repertoire and mutational landscape evolve in responsive vs. non-responsive tumors. Finally, we will obtain a subset of samples that are amenable to analysis of mRNA by RNASeq.

Quantitative multiplexed IHC: Measuring the density, phenotype and location of different cell types: Samples will be obtained from patients at baseline and during ipi/nivo on Day 28 (+/- 7 days) of therapy and fixed in 10% neutral buffered formalin and paraffin embedded according to standard institution protocols. Twenty slides with tissue section cuts of 3-4 um thick will be provided for analysis from each FFPE block. At selected study sites, the biopsy will be processed as fresh frozen tissue for RNASeq and other analyses. Slides will be stained with a set of multiple biomarkers to comprehensively define the innate and adaptive immune system in tumors and the functional characteristics of different cells in the tumor microenvironment. Note that each antibody used is an in vitro diagnostic antibody used for IHC, meets the highest level of sensitivity and specificity requirements, and have been optimized for single staining and multiplexed staining in our lab. Slides will be analyzed using quantitative imaging analysis optimized by the translational as well as previously described. (7, 8)

Lymphocyte receptor sequencing: Defining the T-cell receptor (TCR) repertoire in tumors: Genomic DNA will be isolated from FFPE blocks (or from fresh frozen samples if available) derived from tumor biopsies performed at baseline and at Day 28 (+/- 7 days) of therapy. The V beta and alpha chains of TCRs will be captured using the ImmunoSeq assay as previously described. (9) The analysis will define the repertoire, diversity and clonality of tumor samples.

Whole exome sequencing: Defining the mutational landscape: Genomic DNA will be isolated from FFPE tissue blocks and matched peripheral blood mononuclear cells (PBMCs). This will allow us to differentiate germline variants (non-cancer variants) from non-synonymous mutations (cancer specific). Following whole exome sequencing, the Genome Analysis Toolkit (GATK) and workflow to process the raw dataset for downstream analysis. To ensure accurate identification of non-synonymous mutations, each variant will require discovery identification with at least two variant discovery software tools (MuTect and Vscan2). The analysis will determine the mutation load and provide for further investigation into the spatial diversity of mutations and HLA binding predictions of specific mutations in terms of response.

Consistent with previous publications, preliminary data in melanoma shows that there are patients who show high CD8+ T-cells in tumors despite having a low mutational load. (10,11,12) Conversely, there are patients that lack a CD8+ T-cell response to their tumor but have high mutational load. We anticipate that our approach will lead to defined signatures (TIL, Clonality, Mutation Score) that are driven by clinical relevance. Investigating the density and repertoire of T-cells in terms of mutational burden will allow us to gain insight into the type of mutations that are associated with clinical response.

Objective 3: To identify T-cell poor subtypes associated with response

The T-cell status of tumors represents a key determinant of response to anti-PD1. Tumors infiltrated with T-cells show sensitivity to single agent anti-PD1 but represent a minority of patients. The majority of tumors lack T-cells and are inherently non-responsive to therapy. T-cell poor tumors represent a heterogeneous group and remain poorly defined. A challenge in the field is to develop immunodiagnostics that have the ability to subtype T-cell poor tumors into immune 'activity' signatures that are clinically actionable.

The response rates observed with combination checkpoint inhibition indicate that there is a responsive subgroup within the T-cell poor group that would otherwise be non-responsive to single agent PD1 inhibitor. We propose to define this subgroup by using multi-parameter flow cytometry and multiplexed multi-parameter immunohistochemistry to analyze the peripheral blood and tumor, respectively, within the same patient. In this way we can compare circulating immune cells and tumor infiltrating immune cells within a given patient and according to treatment outcome groups. Immune cell types within the innate the adaptive system will be defined and monitored within the blood and in tumors. Our rationale for this approach is based on the necessary mobilization of TILs from the peripheral blood in order to infiltrate a tumor responding to combination to combination therapy. Our goal is to define the innate and adaptive immune landscape in baseline tumors that are CD8+ T-cell poor but undergo unique alterations during response that are absent in non- responsive tumors.

c. Statistical Plan:

1. Objective 1: Assess the independent prognostic value of baseline T-cell density, T-cell receptor (TCR) clonality, ctDNA fraction, and mutational load in terms of response in each arm.

We will consider each treatment arm separately. Then for each arm, we will assess whether each of the IHC markers, T-Cell clonality, ctDNA fraction, mutational load and mRNA signatures can be used to identify patients who respond. Under our first objective, we will assess each variable individually. In particular, we will use logistic regression to regress dichotomous response status on each variable, one-at-a-time. Since our primary objective is to develop a classification model for identifying responders, we will estimate standard model classification characteristics including misclassification error, sensitivity, specificity, and AUC for each variable where the threshold for the logistic probabilities for defining predicted responder vs. non-responder will be tuned via leave-one-out cross validation (LOOCV). We will estimate both the in-sample classification characteristics as well as the cross-validated (where the full procedure is cross-validated, with potential nested LOOCV for tuning parameter selection) characteristics with corresponding 95% confidence intervals. The in-sample estimates represent optimistic values while the LOOCV estimates represent pessimistic values such that the smallest lower 95% CI and highest upper 95% CI bound for each characteristic on each variable will provide conservative coverage of the true characteristic value. For Arm 1 (ipilumimab alone), with a sample size of 21 patients, assuming we have 90% compliance on tissue submission, then we will be able to estimate the in-sample or cross validated misclassification error to within 22.5% (95% CI). For Arm 2 (combination therapy), with a sample size of 63 patients and again assuming 90% compliance on tissue submission, then we will be able to estimate the in-sample or cross validated misclassification error to within 13.0% (95% CI).

Although our primary analysis will focus on developing classification models, we will also assess the association between response and each individual marker, clonality, mutational load, mRNA expression signature, and ctDNA fraction. The analysis will be again conducted separately by treatment arm. For each of the IHC markers, clonality, and ctDNA fraction, we will test for difference in mean levels between responders and non-responders using two-sample t-tests. We assume we obtain data on 90% of patients and that the response rates are 15% and 30% in arms 1 and 2, respectively. Then at the nominal $\alpha=0.05$ level, we anticipate 80% power to detect a difference in marker level, clonality, or ctDNA fraction between responders and non-responders of 1.9 and 0.83 standard deviations in Arms 1 and 2, respectively. Further, we will also assess whether individual mRNA transcripts and genes are associated with response. Specifically, we will compare the expression between patients who respond and who do not respond using two-sample t-tests again. We will accommodate multiple testing by controlling the false discovery rate. With the same response rate and sample size assumptions as before, and further assuming that 80% of genes are not associated with response, then at the FDR = 5% level, we anticipate 80% power to detect a difference in expression level of 2.43 and 1.33 standard deviations in Arms 1 and 2, respectively. Note that t-tests are used since they can be more powerful than logistic regression, but for all association analyses in this objective and subsequent translational medicine objectives, we will consider the use of alternative approaches, e.g. data transformation, Wilcoxon tests or logistic regression, if there are outliers or influential points.

Since mutational load is far from normally distributed, we will use a Wilcoxon test to test for difference in mutational burden. To assess power, we conducted simulations under the assumption that we will collect exome sequencing data on 90% of patients and that we will control the type I error rate at the two-sided $\alpha=0.05$ level. To simulate mutational load, we used an internal, private data exome sequencing data set comprised of 13 non-responder patients to first line anti-PD1 therapy and sampled from the interpolated empirical cumulative distribution function (ECDF) via the inverse probability integral transform. For power analyses, data from this distribution were taken to be null. To simulate under the alternative, we shifted all of the mutational load values by a scalar δ and re-sampled from the interpolated ECDF of the shifted data. For Arm 1, assuming response rate of 15%, with 18 total patients, we anticipate 80% power to detect a shift in mutational load distribution of $\delta=13.9$. For Arm 2, assuming response rate of 30%, with 54 total patients, we anticipate 80% power to detect a shift in mutational load distribution of $\delta=2.7$. We again emphasize that alternative approaches will be considered if Wilcoxon tests do not perform well, e.g. due to heteroscedasticity etc.

2. **Objective 2:** Prognostic Value of T-cell Density, TCR Clonality, and Mutational Load

We will assess the joint capacity of the IHC markers, T-Cell clonality, ctDNA fraction, and mutational load, and gene expression signatures to identify patients who respond to each therapy. In particular, analyzing each arm separately, we will use the logistic elastic net to model the joint effect on response of the multiple markers and variables simultaneously. We will select the tuning parameters for elastic net via a two-dimensional grid search and LOOCV. We will again estimate the in-sample and cross-validated (of the entire procedure with nested LOOCV for tuning) model classification characteristics and corresponding 95% confidence intervals, again noting that these represent optimistic and pessimistic bounds for each characteristic. Since the elastic net essentially enforces linearity in the effects of the variables, we will also consider the use of alternative strategies, including large margin (e.g. support vector machines) and tree based classifiers in order to accommodate potential nonlinear and potentially interactive effects. Independent of the specific classification method used, for Arm 1, with a sample size of 21 patients and again assuming we have 90% compliance on tissue submission, then we will be able to estimate the in-sample or cross validated misclassification error to within 22.5% (95% CI). For Arm 2, with a sample size of 63 patients, 90% compliance on tissue submission, then we will be able to estimate the in-sample or cross validated misclassification error to within 13% (95% CI)

3. **Objective 3:** Identification of T-cell Poor Subtype(s) Associated with Response

We will first define the range of CD-8+ T-cell density in the tumor sample characterizing a patient as T-cell poor using a supervised approach: this range is currently undefined for patients who have already failed on an anti-PD1 or anti-PD-L1 agent. Specifically, we will consider a range of thresholds for CD8 expression above which the patients are classified as T-cell rich and below which patients are classified as T-cell poor. For each candidate threshold, we will estimate the proportion of responders above and below the threshold. The final threshold defining T-cell poor status will be selected as the threshold which leads to the highest difference in

proportion of responders above vs. below the threshold. We will also consider un-supervised approaches based on identifying gaps in the distribution of CD8 expression and will tune this according to our supervised results.

After defining the range characterizing patients as T-cell poor, we will restrict further analyses to the patients determined to be T-cell poor. We will then repeat the approach used in Objective 2 to develop a signature identifying T-cell poor patients who respond to therapy. We will again estimate the in-sample and cross validated classifier operating characteristics and construct 95% confidence intervals. Assuming that 90% of patient samples are available for analysis, for Arm 1, we will be able to estimate the in-sample or cross-validated misclassification error to within 25.2%, 23.7%, or 23.1% (95% CI) if 80%, 90%, or 95%, respectively, of patients are determined to be T-cell poor. For Arm 2 we will be able to estimate the in-sample or cross-validated misclassification error to within 14.6%, 13.7%, or 13.4% (95% CI) if 80%, 90%, or 95%, respectively, of patients are determined to be T-cell poor.

We will repeat this analysis using the data collected from blood samples.

References for 18.1

- 2 Morrison C. 'Financial toxicity' looms as cancer combinations proliferate. *Nat Biotechnol* 33:783-4, 2015.

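### Leave-one-out AUC in Appendix 18.1c is biased downward by an artefact (a useless single marker averages about 0.3 in Arm 2, an empty model scores 0); use leave-pair-out for AUC instead

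*Combined protocol and SAP*

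**What the plan says.** Appendix 18.1c, Objective 1, analyses each arm separately: "we will use logistic regression to regress dichotomous response status on each variable, one-at-a-time". The characteristics to be estimated are "misclassification error, sensitivity, specificity, and AUC for each variable". Each is estimated in-sample and by cross-validation, "where the full procedure is cross-validated, with potential nested LOOCV for tuning parameter selection". Leave-one-out is the only resampling scheme named.

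The plan then states: "The in-sample estimates represent optimistic values while the LOOCV estimates represent pessimistic values". From this it concludes that "the smallest lower 95% CI and highest upper 95% CI bound for each characteristic on each variable will provide conservative coverage".

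Objective 2 repeats the scheme for a logistic elastic net tuned by leave-one-out: "model classification characteristics and corresponding 95% confidence intervals, again noting that these represent optimistic and pessimistic bounds for each characteristic". Objective 3 does so in the T-cell-poor subset: "We will again estimate the in-sample and cross validated classifier operating characteristics".

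The plan does not say how a cross-validated AUC is formed from leave-one-out predictions, names no interval method for it, and gives no precision figure for AUC.

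**The concern.** An AUC compares responders with non-responders. A left-out set of one patient contains only one of the two, so no AUC exists within it. The natural way to obtain a leave-one-out AUC is to pool the held-out predictions from all the fitted models and rank them together.

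Those models differ systematically. The model that scores a responder was fitted with one responder fewer, and so has a lower fitted response rate. The model that scores a non-responder was fitted with one non-responder fewer, and so has a higher one. If the marker carries little information, this shift in the intercept decides the ranking, and it always goes against the responders. The result is an artefact of pooling. Ordinary pessimism from a slightly smaller training set would leave a useless marker near 0.5.

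At stake are the AUC estimates of the marker and joint-model objectives. Section 11.1 counts biomarker assessment among the study's major additional objectives. A point estimate of 0.3, or 0, also invites the false reading that a marker predicts non-response.

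**Working it through.** **Inputs.** Objective 1 gives, for Arm 1, "with a sample size of 21 patients, assuming we have 90% compliance on tissue submission", and for Arm 2 63 patients with the same compliance. It assumes response rates of 15% and 30%.

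- Arm 1: 21 × 0.90 = 18.9, about 19; 0.15 × 19 = 2.85, about 3 responders and 16 non-responders.
- Arm 2: 63 × 0.90 = 56.7, about 57; 0.30 × 57 = 17.1, about 17 and 40.
- Section 11.1 assumes 25% in the combination arm, which gives 14 and 43; this was run as a sensitivity case.
- Detectable effects in Objective 1: 1.9 SD (Arm 1) and 0.83 SD (Arm 2).

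**The plan's own figure.** The half-width for misclassification error is 1.96 × √(0.25/n): 22.5% for n = 19 and 13.0% for n = 57. Both stated figures reproduce.

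**Empty model (exact).** With r responders in n and no variable kept, a left-out responder is predicted at (r − 1)/(n − 1) and a left-out non-responder at r/(n − 1).

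- Arm 2: 16/56 = 28.6% against 17/56 = 30.4%.
- Arm 1: 2/18 = 11.1% against 3/18 = 16.7%.

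Every responder ranks below every non-responder, so AUC = 0 in both arms.

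**Single markers (simulation).** A normal marker was shifted by δ SD in responders, so that true AUC = Φ(δ/√2). The logistic model was refitted n times and the held-out predictions were pooled. There were 600 data sets per setting, and 150 for leave-pair-out, in which each responder/non-responder pair is left out together and scored by one model. Intervals are Hanley-McNeil, which is an assumption. The combined interval is the plan's rule.

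| Arm (resp./non-resp.) | δ | True | In-sample | Leave-one-out | Leave-pair-out | Combined coverage |
|---|---|---|---|---|---|---|
| 2 (17/40) | 0 | 0.50 | 0.57 | 0.32 | 0.52 | 99% |
| | 0.5 | 0.64 | 0.64 | 0.53 | not run | 99% |
| | 0.83 | 0.72 | 0.72 | 0.66 | 0.72 | 97% |
| | 1.33 | 0.83 | 0.83 | 0.80 | not run | 97% |
| | 1.9 | 0.91 | 0.91 | 0.89 | not run | 98% |
| 1 (3/16) | 0 | 0.50 | 0.64 | 0.23 | 0.52 | 98% |
| | 0.5 | 0.64 | 0.68 | 0.32 | not run | 98% |
| | 0.83 | 0.72 | 0.74 | 0.42 | 0.65 | 98% |
| | 1.33 | 0.83 | 0.82 | 0.59 | not run | 92% |
| | 1.9 | 0.91 | 0.91 | 0.75 | not run | 87% |

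With 14/43 in Arm 2, the useless marker averages 0.31 (leave-pair-out 0.49) and the 0.83 SD marker 0.66 (leave-pair-out 0.72). Repeat runs gave 0.30 to 0.32 for the useless marker in Arm 2 and 0.24 in Arm 1. They gave 0.53 to 0.57 for a true AUC of about 0.65 in Arm 2, and up to 0.68 at 0.83 SD.

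The leave-one-out interval taken alone covers the truth for a useless marker in 53% of data sets in Arm 2 and 41% in Arm 1. The combined interval for a useless marker averages 0.53 wide in Arm 2, against 0.33 for the in-sample interval. In Arm 1 it averages 0.89.

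**Joint models (smaller runs, Arm 2, 17/40).**

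- Five useless variables, unpenalised, averaged 0.45.
- Elastic net, eight variables, mixing 0.5, penalty tuned by leave-one-out at a single level, 60 data sets: with no signal, 68% chose the empty model and reported 0. With two markers informative at 0.5 SD each, 25% still reported 0, while the median was 0.64.
- Ridge as a stand-in for the elastic net, nested tuning, eight markers with two informative at 0.83 SD, 372 data sets: mean 0.68, with 7% below 0.5.

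**The case against.** The plan already labels the leave-one-out value pessimistic and never relies on it alone. It pairs it with the in-sample value and takes the outer limits of both intervals. In Arm 2 that rule did cover at least 95% of the time in every setting, so the coverage claim holds there. What it costs in Arm 2 is width. In Arm 1 coverage itself fails for strong markers.

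A reader might infer that real markers will look worthless. The documents do not support this. At the plan's own detectable effect in Arm 2 the AUC is lowered but clearly above 0.5, and strong Arm 2 markers lose little. At Arm 1's 1.9 SD the mean is still about 0.75. Only weak markers, and Arm 1 markers of about 0.83 SD or less, fall close to or below chance.

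A reader might also infer that the marker objectives will be answered wrongly. That goes too far. AUC is one of four characteristics, and the stated precision concerns misclassification error. Association with response is tested separately in 18.1c by t-tests, Wilcoxon tests and false-discovery-rate control, and in Section 11.3 by a t-test. None of these uses a cross-validated AUC.

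Nor does it follow that a penalised joint model scores 0 whenever it is fitted. That happens when no variable is kept or when a very strong penalty is fixed in advance. Objective 2 tunes the penalty, and the tuned runs gave 0 in only some data sets.

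Finally, pooling is inferred, because the plan does not say how the AUC is formed. But leave-one-out offers no within-fold alternative, and the plan names no other scheme.

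**Conclusion.** The point stands for AUC only. Pooled leave-one-out AUC is biased downward: about 0.3 in Arm 2 and 0.24 in Arm 1 for a useless single marker, and exactly 0 for a model that keeps no variable.

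- **Severe** for weak markers (Arm 2, true about 0.65: 0.53 to 0.57) and in Arm 1 (true 0.72: about 0.43; true 0.91: about 0.75).
- **Modest** at Arm 2's planned 0.83 SD (0.66 to 0.68 against 0.72).

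The combined interval keeps at least 95% coverage in Arm 2 by becoming much wider, and drops to 87-92% at 1.9 and 1.33 SD in Arm 1.

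The zero for an empty model is arithmetic. The other figures assume normal markers, fixed responder counts and near-unpenalised logistic fits, and coverage assumes Hanley-McNeil intervals. The joint-model runs were small or used a stand-in, and the T-cell-poor subset was not simulated.

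**What to change.** In Appendix 18.1c, Objectives 1 to 3, replace leave-one-out with leave-pair-out cross-validation for AUC in both arms. Repeated stratified k-fold, averaged within fold, is acceptable in Arm 2 only: with about 3 responders in Arm 1, five folds would leave at least two without a responder, and AUC would again be undefined there. Remove AUC from the statement that leave-one-out gives a pessimistic bound with conservative coverage. Leave-one-out can stay for misclassification error.

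The AUC interval method should be named at the same time. A simple bootstrap in Arm 1 would draw no responder in about (16/19)^19 = 4% of resamples.

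Leave-pair-out is not free of error in Arm 1: at 0.83 SD it averaged 0.65 against 0.72. It does remove the artefact, since a useless marker centres near 0.5.

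The cost is a change of wording, a few lines of code and more model fits. Arm 2 needs 17 × 40 = 680 pairs against 57 single deletions, about 12 times as many, and more with nested tuning. Arm 1 needs 3 × 16 = 48 against 19. No patient, sample or visit is added.
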